Memory and Attention Adaptation Training-Geriatrics (MAAT-G) is a cognitive behavioral therapy-based intervention for targeting modifiable factors of CRCD for older adults.²⁰⁻²³ MAAT-G provides instruction and practice with adaptive behavioral coping skills, stress management techniques, and compensation strategies for episodes of cognitive failure (e.g. lapses in memory, attention). MAAT-G is derived from an existing CRCD intervention (MAAT), and was adapted for the unique needs of older adults. MAAT-G is a series of ten manualized workshops delivered by a trained clinician (e.g. psychologist, psychology post-doctoral fellow, psychology intern or Research Nurse) via video-conferencing combined with a participant workbook. In younger cancer survivors (i.e. those who have completed chemotherapy), the original MAAT intervention was shown to improve self-perceived cognition (Functional Assessment of Cancer Therapy—Cognition [FACT-Cog], $d=0.52$), verbal memory (California Verbal Learning Test 2 (CVLT), $d=-0.63$) and processing speed (Symbol Digit Subtest of Telephone Based Neuropsychological Status [TBANS], $d=0.5$).^{11,26} These cognitive functions are particularly important for older adults; and we propose to deliver MAAT-G alongside systemic cancer therapy to mitigate the development of CRCD (when risk is highest) and CRCD-related effects on functional independence for older adults.

Study Objective:

Primary Objective:

- Examine the preliminary effect of MAAT-G on FACT-Cog.
 - Hypothesis: Patients receiving MAAT-G will have better perceived cognition (FACT-Cog) compared to control at follow-up.

Secondary Objectives:

- Estimate MAAT-G's effect on function (e.g. IADL) and objective neuropsychological measures including CANTAB, FACT-Cog, COWA, HVLT-R, GDS, Brief Test of Adult Cognition by Telephone (BTACT), and GAD-7.
 - Hypothesis: Patients receiving MAAT-G will have better short-term visual/spatial memory, sustained attention, visual memory/new learning, verbal fluency, verbal learning and memory, and function compared to control at follow-up.
- Develop a more complete understanding of the patient and caregiver experience with MAAT-G and their perceptions of MAAT-G's benefits on cognition and function beyond what is captured by quantitative measures alone, through integration of quantitative

data with semi-structured interviews.

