7.0 TREATMENT PROTOCOL

7.1 Measures:

Patient measures will include *demographics, cognitive, psychological, and functional independence* measures. The battery was selected based upon our experience in prior studies.^{1,26,50,51} Based upon experience in prior studies, we estimate the cognitive evaluation will take approximately 60 minutes to complete^{1,3} and the demographics, psychological and functional independence measures will take approximately 20 minutes.

Demographics: Patient and caregiver demographics will be collected, including age, gender, race, ethnicity, marital status, education and socio-economic status will be captured. Cancer and treatment variables, comorbidities, and medications list will be collected from the medical record by study staff.

Cognitive Evaluation will include: 1) FACT-Cog⁵², a validated patient reported outcome measure created to assess cognitive challenges identified by patients with cancer; 2) Brief Test of Adult Cognition by Telephone⁷⁹ (BTACT), a slightly modified version that assesses multiple dimensions central for effective functioning across adulthood; 3) Cambridge Neuropsychological Test Automated Battery (CANTAB) delayed match to sample test⁵³ (DMS), Rapid Visual Information Processing (RVP), and Paired Associates Learning (PAL), validated, computerized tests that assess short- term visual/spatial memory, sustained attention, and visual memory/new learning; 4) Controlled Oral Word Association (COWA)⁵⁴, a measure of verbal fluency evaluating expressive language and executive function; and 5) Hopkins Verbal Learning Test-Revised (HVLT-R)⁵⁵, a validated test of verbal learning and memory. All measures are “paper and pencil”, except for the CANTAB (computer-based assessments that, due to COVID-19, will be administered virtually by collecting patients’ emails and sending a web- based link). COWA, HVLT-R, and BTACT require the study coordinator to administer the tests; they can be administered virtually so study coordinator will schedule a telephone or televideo meeting with the patient at the corresponding time points, as needed.

Psychological Assessment: will include Geriatric Depression Screen (GDS)⁵⁷, Generalized Anxiety and Depression (GAD-7)⁵⁸, and Intolerance of Uncertainty Scale-Short Form (IUS-12). IUS-12 will be administered by the study coordinator over the phone or via televideo (Zoom application) at the appropriate time points.

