Quantitative Data Analysis: Underlying assumptions to all statistical analyses will be checked using appropriate graphical and numerical methods.⁷² In the case of serious violation of assumptions, appropriate transformations or nonparametric methods will be used.^{73,74} If outlying observations are encountered, data will be checked. If no errors are found, we will conduct analyses with and without the outlying data and compare results. Bivariate associations between treatment group and participant variables (demographics, cancer and treatment characteristics, baseline assessment of outcome measures) will be examined to assess possible imbalance between arms. Since this is a pilot study, will use significance level=0.10 to avoid false negative results, and decrease the risk of abandoning a promising intervention.^{75,76}

Analysis of the primary outcome: To assess the impact of the intervention on patient-reported cognition (FACT-Cog), we will employ the analysis of covariance (ANCOVA). The model will consist of post-FACT-Cog as the outcome and include the arm as the main effect and pre-FACT-Cog as a covariate. We will evaluate the interaction between pre-FACT-cog and the arm. We will adjust for baseline covariates in case that imbalance between arms was detected, and baseline and change in psychological measure (GDS and GAD-7). All non-significant covariates will be removed from the model.

Analysis of secondary and exploratory outcomes: The effect of MAAT-G on objective cognition (CVLT-R, TBANS, CANTAB, COWA, HVLT-R, TMT A/B), functional independence (IADL) and stress response (cortisol) will be assessed with the same strategy as for the primary outcome.

As above, a sample size of 85 patients is planned based upon anticipated attrition rates. If attrition of patients occurs at a higher proportion than anticipated during the trial conduct, we will conduct an interim data analysis check to assess for need in adjusting sample size.

Phase II Qualitative Data Analysis: Semi-structured interviews will be prepared and coded similar to Phase Ib. Potential themes from Phase II interviews include experiences of cognitive failure and perceived timing and mode of onset of symptoms, changes in functional independence, perception of how the intervention (either MAAT-G or ST) influenced symptoms and experience, and experiences with the adaptive behavioral or compensatory techniques used.

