Estimate the effect of MAAT on FACT-Cog, objective measures of cognition and functional independence and explore through semi-structured qualitative interviews, the patient and caregiver experience with MAAT-G and perception of how MAAT-G influences daily functioning and perceived benefits.	
 Cognitive Assessment (Quant): Perceived: FACT-Cog Objective: Neuro-psychological assessment battery Functional Independence (Quant): IADL Semi-structured interviews (Qual) 	
 Descriptive statistics, t-tests, chi-square tests, logistic regression Theme analysis guided by Phenomenology 	
Merging: Qual and Quant are brought together for analysis
 
Purpose: To use qual data to help explain the quant outcomes; to understand in more depth how the conceptual model mechanism worked; to assess the context when comparisons of outcomes are made with baseline data.
	We will compare themes between patients who report longitudinal improvement in perceived cognition versus those who report longitudinal decline and we will compare themes between study arms. (e.g. patients with longitudinal improvement in perceived cognition or those receiving MAAT-G may report a greater ability to manage the complex schedule of cancer treatments or a greater ability to participate in social roles such as caregiving for a spouse or volunteer activities).

8.3. Records to be Kept:

8.3.1. Data Collection Table:

FORM	SCHEDULE OF DATA COLLECTION	
	Baseline	Post-Intervention
On Study Data (Patient and caregiver demographic information and clinical data)	X	
FACT-COG	X	X
CANTAB	X	X
BTACT	X	X
COWA	X	X
HVLT-R	X	X
	X	X
GAD-7	X	X
IADL Survey	X	X
TUS-1Z	X	X

8.3.2 All hardcopy research records will be stored onsite in the University of Rochester Medical Center, in locked research files at the James P. Wilmot Cancer Center. The Cancer Center is secured with electronic key cards. Offices within the Cancer Center are again secured by key and data is kept in locked file cabinets. Electronic research records are stored on the University of Rochester Medical Center's password secured and firewall protected networks. These are the same methods of security used for patient medical records. All study data will be kept for a period of 10 years after the study and all reports and publications are complete.

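### The secondary models in 8.2 adjust for post-randomisation change in GDS and GAD-7, and the secondary outcome list does not match the measures listed as collected or the secondary objective

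*Combined protocol and SAP*

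**What the plan says.** The secondary paragraph of 8.2 reads: "The effect of MAAT-G on objective cognition (CVLT-R, TBANS, CANTAB, COWA, HVLT-R, TMT A/B), functional independence (IADL) and stress response (cortisol"), and says that these "will be assessed with the same strategy as for the primary outcome".

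The primary strategy, set out just before it, is an ANCOVA of post-intervention FACT-Cog on arm and baseline FACT-Cog, with a check of the arm-by-baseline interaction. It adjusts for baseline covariates found to be imbalanced and for "baseline and change in psychological measure (GDS and GAD-7"). Then "All non-significant covariates will be removed from the model".

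The secondary objective in section 2.0 is to estimate the effect of MAAT-G on function (IADL) and on "objective neuropsychological measures including CANTAB, FACT-Cog, COWA, HVLT-R, GDS, Brief Test of Adult Cognition by Telephone (BTACT), and GAD-7".

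Section 7.1 (Measures) gives the patient measure groups as "demographics, cognitive, psychological, and functional independence". Its cognitive evaluation numbers five instruments: FACT-Cog, BTACT, CANTAB (three tests), COWA and HVLT-R. The psychological measures are GDS, GAD-7 and IUS-12, and the functional measure is IADL. Table 8.3.1 agrees as far as it can be read.

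**The concern.** There are two problems in one paragraph.

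The more important one is the covariate set. Change in GDS or GAD-7 is known only after treatment, and MAAT-G teaches relaxation and coping skills that could well alter it. Conditioning on a variable that the intervention may move removes, or adds, the part of the effect that is associated with it. The objective asks for the effect of MAAT-G on each measure. If mood moves, the coefficient from this model answers a different question.

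The other is the outcome list. Followed literally, 8.2 commits the trial to analyses of four measures for which the protocol describes no collection, and gives no outcome model for two scales that the objective names. A later reader could not tell whether results on CVLT-R, TBANS, TMT or cortisol were never obtained or were left out. The model for GDS and GAD-7 could be chosen after the data are seen.

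The two problems interact. If the list were repaired merely by adding GDS and GAD-7 under the existing strategy, each would be regressed on its own change.

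**Working it through.** **Step 1: compare the lists.** CANTAB and TMT A/B are counted as one measure each.

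| Measure | Objective (2.0) | 7.1 | Table 8.3.1 | Role in 8.2 |
|---|---|---|---|---|
| CANTAB, COWA, HVLT-R, IADL | yes | yes | yes | secondary outcome |
| FACT-Cog | yes | yes | yes | primary outcome |
| BTACT | yes | yes | yes | not named |
| GDS | yes | yes | row label lost | covariate only |
| GAD-7 | yes | yes | yes | covariate only |
| IUS-12 | no | yes | label garbled | not named |
| CVLT-R, TBANS, TMT A/B, cortisol | no | no | no readable row | secondary or exploratory outcome |

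Results:
- 8.2 list: 8 measures, of which 4 are listed as collected and 4 are not. If CANTAB is counted as three tests and TMT as two, 5 of 11 are not.
- Secondary objective: 5 of 8 measures have a named outcome analysis (CANTAB, COWA, HVLT-R, IADL, FACT-Cog), 2 of 8 have none (GDS, GAD-7), and 1 of 8 (BTACT) is unnamed.

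Elsewhere, a CVLT version and TBANS appear only as outcomes of earlier MAAT studies (2.0 and 3.6d). Cortisol appears only as background on etiology (2.0 and 3.3), with no sampling described. TMT is named nowhere else. The row of 8.3.1 with the lost label is a single row, and GDS is the only 7.1 measure without a recognisable one.

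**Step 2: effect of adjusting for change in mood.** The plan states no figure for this, so there is none to reproduce. With baseline mood in the model, adjusting for change is equivalent to adjusting for the post-intervention mood score. For one mood scale, with outcome and mood in SD units and the same pre-post correlation,

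adjusted arm coefficient = d − ρ × m,

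where d is the true arm effect on the outcome, m the arm effect on the mood score, and ρ the residual correlation between outcome and mood score.

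Inputs: d = 0.52, borrowed from the effect size in 8.2 and assumed here for a secondary outcome; m of 0.3 to 0.5 SD in either direction and ρ of -0.3 to -0.5, both assumed. Higher mood scores mean worse mood, and higher outcome scores mean better cognition.

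- Mood scores fall: 0.52 − (−0.3)(−0.3) = 0.43; 0.52 − (−0.5)(−0.5) = 0.27.
- No mood effect: 0.52 − 0 = 0.52.
- Mood scores rise: 0.52 − (−0.3)(0.3) = 0.61; 0.52 − (−0.5)(0.5) = 0.77.

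A simulation with 35 per arm, pre-post correlation 0.5 (both from 8.2) and 4,000 runs agreed with these values to about 0.01. Applying the plan's removal of non-significant covariates as well, at the 0.10 level, gave 0.45 to 0.28, 0.52, and 0.60 to 0.77, so that rule does not cure the problem. ANCOVA on the outcome's own baseline returned 0.52 throughout.

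**Step 3: a mood scale as its own outcome.** Post = baseline + change exactly. A model with baseline and change as covariates therefore fits perfectly, with coefficients 1 and 1 and an arm coefficient of 0. In simulation with an assumed effect of -0.50 SD on GDS, own-baseline ANCOVA returned -0.50; adding change in GDS returned 0.00 with R-squared 1.00.

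**The case against.** **The list mismatch is close to clerical.** This largely stands. CANTAB, COWA, HVLT-R and IADL reach every domain in the secondary hypothesis, which names no mood domain, and the study calls itself a pilot. BTACT, described as "a slightly modified version that assesses multiple dimensions central for effective functioning across adulthood", sits in the cognitive evaluation of 7.1 and may fall under objective cognition without being named. The mismatch alone would be a minor tidy-up.

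**The four measures may be collected after all.** A reader might infer that there will be no data on them. The documents do not go that far: the study schema is not shown, and 8.3.1 is a table of forms, so a missing biological sample weighs less there than a missing questionnaire. What can be said is that they are not listed as collected. The word exploratory in the paragraph title does not settle it, since no exploratory objective is stated and exploratory analyses also need data.

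**GDS and GAD-7 might go unreported.** A reader might infer this, but section 2.0 already commits the trial to estimating effects on both. Only the model is open.

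**Table 3 might seem to contradict 8.2**, because it lists "Descriptive statistics, t-tests, chi-square tests, logistic regression" and not ANCOVA. It is the mixed-methods integration plan, and those methods may serve that purpose. It is not evidence of a conflict. Nor does the reference list, where a paper on test norms is not cited in the readable text, show that a test was deleted.

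**The mood adjustment may be intended, and its bias rests on assumptions.** Wanting to know whether cognition improves beyond any change in mood is a fair question. It is not the one in the objective, and answering it requires no unmeasured common causes of mood and cognition. The size in Step 2 is assumed, and with no mood effect there is no shift. The direction is open too: 7.3 allows that participation could increase stress. But the plan cannot rely on mood being unaffected while naming GDS and GAD-7 as measures on which an effect will be estimated.

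**Conclusion.** The point holds. As written, the secondary models adjust for a post-randomisation quantity that the protocol itself treats as an outcome. The arm coefficient then misses the total effect of MAAT-G by the residual correlation times the mood effect: 0.09 to 0.25 SD either way under the assumed ranges, against a true 0.52, and zero if mood does not move. This is the part that matters most. The ranges assume one mood scale; the plan adjusts for two.

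The list conflict is also established: 4 of 8 measures are not listed as collected, 2 of 8 objective measures have no outcome model, BTACT is covered only by inference, and IUS-12 is collected but is in neither the objective nor 8.2.

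A reader might infer that the list conflict weakens the primary analysis or the sample size. It does not. The covariate sentence does reach the primary model, but that is a separate route. A reader might also infer that 8.2 already plans to regress GDS or GAD-7 on its own change. It does not; that would arise only if the list were extended without changing the strategy.

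**What to change.** 1. **Covariates.** In all arm-effect models, remove change in GDS and GAD-7 and keep their baseline values. The same sentence governs the primary FACT-Cog model, so make the same change there. A model that includes change in mood may be kept as a labelled exploratory analysis.

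2. **Outcome list.** Remove CVLT-R, TBANS, TMT A/B and cortisol from 8.2 or, if they are collected, add them to 7.1 and 8.3.1. Name BTACT. Give GDS and GAD-7 an outcome model that never includes their own change. Labelling IUS-12 exploratory is optional.

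Suggested wording:

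> Secondary outcomes are BTACT, CANTAB, COWA and HVLT-R (cognition), IADL (function), and GDS and GAD-7 (mood). Cognition and function scores will each be analysed by ANCOVA of the post-intervention score on arm and the measure's own baseline, with baseline GDS and GAD-7 as further covariates. GDS and GAD-7 will each be analysed by ANCOVA on arm and own baseline. The interaction check, the adjustment for imbalanced baseline covariates and the covariate-removal rule are as for the primary outcome. No arm-effect model will include change in GDS or GAD-7.

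This leaves the rule on removing non-significant covariates as it is; if the sponsor alters that rule, the change should be stated openly.

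**Cost.** Wording only. Sample size and data collection do not change. If the four measures are in fact collected, the list edits move to 7.1 and 8.3.1.

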9.0 DATA SAFETY AND MONITORING

This protocol should be considered low risk as the intervention is a cognitive behavioral therapy (CBT)-based intervention. CBT- based treatments are utilized in routine clinical care for use with community dwelling older adults. This study is designed to see if MAAT, a CBT-based intervention, is feasible to deliver to older adults receiving systemic cancer therapy for breast cancer and can improve cognitive outcomes for this population.

9.1. Adverse Event Reporting Requirements:

9.1.1. Adverse events will be reported using the URCC Adverse Event form and/or as required by the Cancer Center Clinical Trials Office.

9.1.2. Adverse events will be reported in accordance with the following guidelines. We will not report adverse events if it is not required per the guidelines.

	Grade 1	Grade 2		Grade 3				Grade 4		Grade 5		
	Unexpected and	Unexpected		Expect	Unexpected		Expected		Unexpect	Expect	Unexpect	Expect
		with hospit	witho ut		with hospit	witho ut	with hospit	witho ut				
Unrelated Unlikely	Not Required	Not Required	Not Required	Not Required	Not Required	Not Required	Not Required	Not Required	10 Calendar Days	Not Required	10 Calendar Days	10 Calendar Days
Possible Probable	Not Required	10 Calendar	Not Required	Not Required	10 Calendar	10 Calendar	Not Required	Not Required	24-Hour; 5	10 Calendar Days	24-Hour; 5 Calendar	10 Calendar Days

Hospitalization is defined as initial hospitalization or prolongation of hospitalization for ≥ 24 hours, due to adverse event.

9.1.3. Adverse event reports will be submitted in one of the following ways:

- (1) By email: (pdf)

(2) By mail:

(3) By fax:

9.1.4. An unexpected adverse event is defined as any adverse experience, the specificity or severity of which is not consistent with the risk information. This is a low risk study as interventions have been shown to improve outcomes of community-dwelling older adults.

9.1.5. A serious event refers to any event in which the outcome results in any of the following: death, a life-threatening adverse experience, inpatient hospitalization or prolongation of existing hospitalization, a persistent or significant disability, incapacity, or a congenital anomaly/birth defect. Important medical events that may not result in death, be life-threatening, or require hospitalization may be considered a serious adverse drug experience when, based upon appropriate medical judgment, they may jeopardize the participant and may require medical or surgical intervention to prevent one of the outcomes listed in this definition. We anticipate that any serious events will be related to standard of care cancer treatment and not due to the MAAT-G intervention, which is designed to improve outcomes and focus on cognitive side effects of cancer treatment. To reiterate, only adverse events attributed to the behavioral intervention will be captured and reported.

9.1.6. Adverse events will be reported in accordance with institutional policies (University of Rochester, Research Subject Review Board, local IRB, URCC CCOP, CTO, and DSMB) as per their requirements.

9.1.7. For patients randomized to ST arm who elect to receive MAAT-G after completion of all study procedures, we will continue to monitor for AE during the time period that they are continuing. To reiterate, only adverse events attributed to the behavioral intervention will be captured and reported.

9.2. Data Safety Monitoring:

9.2.1. All adverse events requiring reporting will be submitted to the current Project Coordinator as described in Section 9.1. Serious adverse event reports will be forwarded to the study chair and the Data Safety and Monitoring Committee (DSMC). Adverse events are entered into a protocol-specific spreadsheet.

9.2.2. Adverse event rates are monitored utilizing the spreadsheet. If a serious adverse event is reported frequently, the study chair will conduct a detailed review. The DSMC Committee Chair will be notified and will determine if further action is required.

9.2.3. The Data Safety Monitoring Committee (DSMC) will review study progress and cumulative reports of adverse events at annual meetings and as needed. An overall assessment of accrual and adverse events will enable the committee members to assess whether significant benefits or risks are occurring that would warrant study closure.

9.2.4. The URCC will notify the other sites immediately of any serious safety concerns identified by the DSMC.

